This pilot study will recruit 30 patients who are in hospital with a confirmed pleural infection from 4 UK centres over an 8 to 10 month period. The patients will be randomised (assigned by computer) to the standard treatment pathway or treatment driven by the RAPID risk stratification score. We will follow patients for up to 3 months. We will measure whether this approach to treatment decisions is acceptable to patients and doctors and whether the study answers the key questions. This will help us know if a larger, definitive study is possible.

We will also interview around 12 patients who are willing to be part of the study, and some who decide not to participate to understand what is important to them when treating this disease and their reasons for taking part or not. Additionally, we will interview 6 clinicians to assess their views and the acceptability of the study and to explore any barriers to participation. This will help us understand what should be measured in a larger study to best improve patient care.

We will collect pairs of pleural fluid and blood from all RAPTOR-f participants to measure the biomarkers and assess for microbiology alongside the septations score on the ultrasound scan to evaluate whether rising levels of these biomarkers will predict treatment failure for patients with pleural infection.

The biomarkers include suPAR (Soluble Urokinase Plasminogen Activator Receptor), PAI-1 (Plasminogen-Activator Inhibitor-1), NE (Neutrophil Elastase) and cytokines interleukins (IL) 1 and 2 on both blood and the pleural fluid.

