	15. To assess if levels of pleural fluid and blood biomarkers (suPAR, PAI-1, IL 1+2, and NET) will predict treatment failure	15. The proportion of participants with an elevated level of pleural fluid and blood biomarkers in serial samples taken on day 1 (randomisation day), 3 and 5(post - randomisation) who did not respond to medical treatment.	15. During hospital stay and while the chest drain in situ (optional).
Intervention(s)	In the intervention arm, following randomisation, a baseline RAPID score will		

Intervention(s)

In the intervention arm, following randomisation, a baseline RAPID score will be calculated (see Table 1). According to the score, participants will be allocated into two groups, as outlined below. The subsequent treatment will be determined by the calculated RAPID score.

Low RAPID score group:

- Admission for drainage Therapeutic aspirate or short-term chest tube insertion for 24 hours and subsequent tube removal if there are no features of sepsis syndrome or significant residual collections, see predefined treatment failure criteria below.
- Early discharge home within 24 to 48 hours of admission if they meet the proposed discharge criteria (see page 26) and they will be provided with a 24/7 contact number for the clinical study fellow if they have any concerns.
- Review in clinic within 3days +/- 2 days, if any features of medical treatment failure are present, they will be admitted to hospital and treated as a medium-high risk score group.

Medium – high RAPID score group:

- Admission for drainage Chest tube insertion
- Intrapleural instillation of recombinant human deoxyribonuclease (DNAse) 5mg BD (diluted in 30mls sterile water) and Recombinant human tissue plasminogen activator (tPA, Alteplase) 5-10mg BD (diluted in 30mls sterile water) intrapleural immediately after chest drain insertion if deemed safe and no contraindication e.g. no active bleeding or bleeding disorder.

	 Surgical referral at time of chest tube insertion for consideration of Video Assisted Thoracoscopic Surgery (VATS) or open surgery. 	
Comparator	Standard care and intergroup comparison in the RAPID driven arm.	

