utilisation	12. Number of pleural procedures and days in hospital post randomisation
13. To assess the pattern of computed tomography of the chest in pleural infection e.g., consolidation	13. Computed tomography of the chest to assess for consolidation
14. Radiological changes following treatment	14. Chest x- Ray to assess for pleural thickening
15. To assess if levels of pleural fluid and blood biomarkers (suPAR, PAI-1, IL 1+2, and NET) will predict treatment failure	15. The proportion of participants with an elevated level of pleural fluid and blood biomarkers in serial samples taken on day 1 (randomisation day), 3 and 5 (post - randomisation) who did not respond to medical treatment.

7. Study design

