13. STATISTICS AND ANALYSIS

The plan for the statistical analysis of the study is outlined below. There will not be a separate SAP document in use for the trial, as the analysis is relatively simple.

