13.1. Description of the Statistical Methods

13.1.1. Analysis of the RAPTOR f feasibility study:

Feasibility parameters will be measured and reported, and include:

- Recruitment proportion (number of randomised patients divided by number of eligible patients)
- Randomisation acceptance rate (proportion of patients who are willing to be randomised over those eligible)
- Retention (number of participants who complete intended treatment, number of participants who complete intended follow up)

These will be reported and used to assess whether or not a definitive trial is feasible. Descriptive statistics will be used to describe the demographic characteristics between the two groups. For categorical variables, numbers (and proportions) will be reported for each treatment group and overall. For continuous variables, means and standard deviations (or medians in the interquartile range) will be reported for each treatment group and overall. As this feasibility study is not powered to draw definitive conclusions, comparisons between the two arms for clinical outcomes will be reported using descriptive statistics only. No statistical tests will be carried out. These will be based on multivariable linear (for continuous outcomes) or logistic (for binary outcomes) regression with adjustment for stratification factors and important prognostic factors and will be reported as adjusted differences in means (for continuous outcomes) or proportions (for binary outcomes). Treatment comparisons will be reported for the intention-to-treat population (all randomised participants will be analysed according to their allocated treatment group irrespective of which treatment they actually receive) as treatment effects together with 95% confidence intervals for the two main comparisons: (1) Standard care vs overall RAPID driven treatment (2) Low RAPID driven treatment arm vs moderate to high RAPID driven treatment arm. Compliance to the interventions will be reported.

To establish the feasibility of collecting accurate long-term outcomes in randomised participants, we will present the completeness of the outcomes across the duration of the trial. The outcome measures collected in this study will be used to inform the sample size for the future definitive large-scale phase III RCT if it is feasible to be undertaken.

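### Secondary outcome 15 aims at prediction of treatment failure but is a single proportion with an ambiguous denominator, no cut-off and no contrast group

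*Protocol*

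**What the plan says.** Objective 15 (Protocol, section 6, repeated in the section 3 synopsis) is to assess whether levels of suPAR, PAI-1, interleukins and a neutrophil marker "will predict treatment failure". The matching measure is "The proportion of participants with an elevated level of pleural fluid and blood biomarkers in serial samples" taken on days 1, 3 and 5, "who did not respond to medical treatment". No cut-off for elevation is given, and nothing says whether one raised sample is enough. The lay summary (section 2.2) frames the aim as change over time: "evaluate whether rising levels of these biomarkers will predict treatment failure".

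Section 13 states: "There will not be a separate SAP document in use for the trial". The protocol is therefore the analysis plan. Section 13.1 names two main comparisons, "1) Standard care vs overall RAPID driven treatment (2) Low RAPID driven treatment arm vs moderate to high RAPID driven treatment arm", says "No statistical tests will be carried out", and describes no biomarker analysis.

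Three other passages bear on the point:

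- Research samples are sought from all consenting participants but are optional, and are not taken once a participant has gone home (sections 9.12.1 and 9.12.2).
- Failure has two definitions. The criteria in section 9.7 require a residual collection plus at least one sign of poor response, and are generally applied around 72 hours. Secondary outcome 5 counts non-responders who also required surgery.
- Outcome 5 reports overall failure but is not linked to marker status.

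**The concern.** Prediction is a statement about a contrast: failures against responders, or elevated against non-elevated participants. The measure names neither. Its sentence can be read as a share of failures, a share of elevated participants, or a share of everyone, and these are different quantities. With no cut-off, the number reported also depends on a choice that could be made after the outcomes are known.

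At stake is whether objective 15 can be answered from the outcome as written. A marker raised in nearly everyone with pleural infection should be distinguishable from one that separates failures from responders.

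**Working it through.** The protocol gives no figure for this outcome, so there is none to reproduce. The check asks what each reading yields for a marker unrelated to failure.

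**Inputs**

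- N = 30 (section 13.2). This is a maximum for biomarkers, as sampling is optional.
- Failure rate 20% (section 5): 30 × 0.20 = 6 failures and 24 responders.
- Low-risk share of the RAPID arm 50% (section 13.2): 15 × 0.5 = 7.5, taken as 7. Discharge is within 24 to 48 hours of admission if the criteria are met (synopsis).
- Prevalence p of an elevated marker: not in the documents. Assumption, range 50% to 95%.

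**Reading A: share of failures who are elevated.** For an unrelated marker this has expectation p. The chance that at least 5 of 6 failures are elevated is p⁶ + 6p⁵(1 − p):

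| p | at least 5 of 6 | all 6 |
|---|---|---|
| 50% | 0.11 | 0.02 |
| 70% | 0.118 + 0.303 = 0.42 | 0.12 |
| 80% | 0.262 + 0.393 = 0.66 | 0.26 |
| 90% | 0.531 + 0.354 = 0.89 | 0.53 |
| 95% | 0.97 | 0.74 |

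At p = 90% the outcome reads about 90%, while specificity is 10% and the likelihood ratio is 0.90/0.90 = 1. The result depends on the number of failures: at p = 90%, all or all but one of the failures are elevated with probability 0.97 for 3 failures (10% rate) and 0.78 for 9 (30% rate).

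**Reading B: share of elevated participants who failed (positive predictive value).** For an unrelated marker on day 1 this is about 6/30 = 20% at any p. To interpret it one needs the failure rate in non-elevated participants, which is not part of the outcome. A very common marker also leaves little room to move: at p = 90%, 27 are elevated, and even if every failure is among them the value is only 6/27 = 22%.

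On days 3 and 5 the denominator shrinks because discharged participants are not sampled. If 7 low-risk responders have left and all 6 failures are still sampled, the expected value for the same unrelated marker is 6/(30 − 7) = 6/23 = 26%. If 15 responders have left (illustrative), it is 6/15 = 40%.

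**Reading C: share of all participants both elevated and failing.** This is 0.20 × p, or 10% to 19% for p from 50% to 95%. It is fixed by the two marginal rates.

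**What the contrast adds.** Suppose 6/6 failures are elevated:

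- With 22/24 responders elevated, specificity is 2/24 = 8%, predictive value 6/28 = 21%, likelihood ratio 1/(22/24) = 1.1.
- With 6/24 responders elevated, specificity is 18/24 = 75%, predictive value 6/12 = 50%, likelihood ratio 1/(6/24) = 4.

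Reading A gives 100% both times.

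**Attainable precision.** For 6/6 the exact 95% CI is 54% to 100%. For an AUC of 0.70 with 6 failures and 24 responders, the Hanley–McNeil variance is [0.70 × 0.30 + 5(0.5385 − 0.49) + 23(0.5765 − 0.49)]/144 = 0.0170, SE 0.130, 95% CI about 0.44 to 0.96.

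**The case against.** The plainest grammar is reading B. Responders with an elevated level are then in the denominator, and an uninformative marker gives about 20% on day 1, which would not impress anyone. Outcome 5 reports overall failure, so a reader could set one figure against the other. This stands in part. It confines the binomial figures to reading A, and it means that what is missing under reading B is the non-elevated group, not the responders. It does not rescue the measure: outcome 5 uses a definition that adds surgery, covers all randomised participants and not just those sampled, and is not linked to marker status.

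Two stronger inferences are tempting. One is that a useless marker will look strong however the outcome is read. The documents do not support that: it holds for reading A at high prevalence, and prevalence is assumed. Under reading B it needs the selective sampling on days 3 and 5. The other is that a misleading figure would drive a wrong decision about the definitive trial. The progression table in section 13.1.2 has no biomarker criterion, and the trial outlined in section 13.2 is sized on hospital stay without mentioning biomarkers.

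It is also fair to say that responder data are not excluded by design, since samples are sought from everyone who consents; the defect lies in the wording of the outcome. The gap between 'rising' and 'elevated' is small, because the former is in a lay summary and outcome 15 already refers to serial samples.

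**Conclusion.** The point holds in a limited form. As written, outcome 15 cannot answer its own objective on any of the three readings, and no other section supplies the missing contrast or the cut-off. How misleading the figure could be depends on the reading. Among failures, an uninformative marker of 70% to 90% prevalence gives at least 5 of 6 elevated with probability 0.42 to 0.89. Among elevated participants, it gives about 20% on day 1 and, for example, 26% on days 3 and 5.

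These figures assume that all 30 participants give samples, that 6 fail, that the marker is independent of failure, and, for the 26%, that only low-risk responders are lost. Optional consent, or the definition of failure that adds surgery, could leave fewer than 6 failures. Severity is minor to moderate: this is a secondary outcome of a descriptive feasibility study, and no progression criterion rests on it.

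**What to change.** Reword outcome 15 in sections 3 and 6 as an exploratory, descriptive comparison of biomarker levels, on the continuous or log scale, by sample day, in participants with and without treatment failure. In the same text:

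- State which of the protocol's definitions of failure applies (the section 9.7 criteria or the outcome 5 wording), and use only samples taken before failure. Failure is generally assessed around 72 hours, so some day 5 samples may come after it.
- Give the number sampled in each group on each day, so that loss of discharged participants is visible.
- Make the AUC with 95% CI for the day 1 sample the main summary. Report day 3 and day 5 levels, and change from day 1 for the 'rising' question, as descriptive additions. An AUC for every combination would mean 5 markers × 2 fluids × 3 days = 30 estimates on about 6 failures.
- If a cut-off is used, fix it before assay results are linked to outcome (the study is open-label, so unblinding is not the relevant moment), and report sensitivity and specificity together.

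The cost is a change of wording; the samples and assays are those already planned, and levels with confidence intervals fit the rule against statistical tests. The downside is that, with at most about 6 failures, intervals will be wide and the result can only generate hypotheses.

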9. PROTOCOL PROCEDURES

The following table illustrates scheduled study related procedures and data collection

Procedure		Consent	Innetions	Follo	ow up visits		
	Screening	Baseline/ Randomisation	Inpatient Assessme	3 days¹	14 days	28 days	90 days
			nt(s)	+/- 2 days	+/- 3 days	+/- 3 days	+/- 3 days
Eligibility assessment	X	Х					
Informed consent	X ²	X ²					

Demographics R	х	Х					
Medical history ^R	Х	Х					
Clinical assessment R	Х	X	Х	X	Х	Х	Х
Concomitant medication ^R	X3	X ³					
Imaging routine – chest x ray R		Х			Х	Х	Х
Imaging routine – Thoracic Ultrasound ^R		Х	X (on days 3±1 and 5±1 post randomisatio n)	X	X	X	
Imaging routine – CT chest ^R	X ⁴	X ⁴	X ⁴				
Chest drain insertion or therapeutic aspiration in situ or planned	х	X					
Intrapleural enzyme therapy ^R			х				
Surgery ^R			Х				
Routine clinical bloods	Х	Х	х	Х	х	Х	
Routine pleural fluid ^R	Х						
Randomisation		X					
RAPID score		X ⁵					
Research pleural fluid collection and storage		Xe	X ₆				
Research blood collection and storage		X ⁶	X _e				
Breathlessness and/or pain (VAS) score		X ⁷			X ⁷	X ⁷	X ⁷

QOL: EQ-5D-5L	X ₈			X8	X8	X8
---------------	----------------	--	--	----	----	----

Assessment of functional ability (SF36)			X 9	X 9	X ⁹
Health utilization		Х			
Semi- structured interviews				X ¹⁰	

^R Indicates procedures or data collection that is part of routine care for all patients. The results of these are required to be collected and documented as part of the RAPTOR - f study, hence are included in this table.

¹ This will be applied to the low RAPID score group, please see the protocol for the details

² Informed consent will be taken within the first 24 hours after discussing the study and offering the participant information sheet.

³ If the participant had any antibiotics prior to admission to the hospital or if they are on anticoagulation or antiplatelet.

⁴ CT scan will be conducted as part of the usual care for all participants with pleural infection during the inpatient stay

⁵ The RAPID score will be calculated for the intervention group ONLY following randomisation.

⁶ The research samples (paired pleural fluid and blood) will be collected on day 1 (randomisation day) 0,3 and 5 post- randomisation (with the first week). This is optional, please see the protocol for the details of the process.

⁷ These assessments will take place in person at baseline, 14 days +/- 3, 28 days +/-3 days and remotely in 90 days +/- 3 days, please see protocol.

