The intermediate and high-risk groups have been combined for the treatment algorithm; there are similar numbers of patients in the combined intermediate and high risk group and the low-risk group (7). Patients in this category will be treated as follows:

- 1. **Pleural drainage:** all patients will be admitted to hospital for chest drain insertion and remain in hospital for as long as is clinically required while the tube is in situ. No specific size of drain is specified, and local practice should be followed.
- 2. Broad spectrum antibiotics: see below; IV antibiotics can be given while the patient is admitted.
- 3. Adjunctive therapy:
 - a. Intrapleural enzyme therapy (tPA / DNase) should be started as soon as possible after drain insertion and randomisation, assuming there are no contraindications. if there is no risk of bleeding.

b. In parallel, referral to local thoracic surgical services made at the time of randomisation, and the need for surgery clinically revisited at 48 hours post-randomisation.

c. In patients where there are contraindications to intrapleural enzyme therapy, immediate surgical intervention in suitable patients should be considered.

Standard care arm:

In the standard care group, the RAPID score *will not be routinely calculated*, and all patients will undergo treatment as per current national guidelines (BTS 2023) (1). This is summarized as follows:

- 1. **Pleural drainage:** all patients will be admitted to the hospital for chest drain insertion and subsequent drainage
- 2. Broad spectrum antibiotics: see below
- 3. **Clinical review** of progression will occur 48 to 72 hours after randomisation and initial above treatment. If there is evidence of poor clinical response (on the objective criteria listed below), the patient will be escalated to either intrapleural therapy or surgical intervention according to patient suitability and clinician choice / usual practice.

Treatment applicable to both arms

A number of treatments should be considered best practice and routine management in patients with pleural infection and will be applied to both groups (intervention and standard care). These treatments follow the NHS standard of care for pleural infection and are as follows:

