- 1. **Broad spectrum antibiotics** to cover both aerobic and anaerobic organisms, and according to infection setting (community or hospital acquired infection), to be focused once culture results are available if positive as per local treatment guidelines or policies.
- 2. Intravenous antibiotics should be given during initial admission (if admitted)
- 3. **Switch to oral antibiotics** should occur once there has been a good clinical response with biochemical and radiological improvement, OR if the patient is intended for outpatient treatment (e.g. low RAPID group).
- 4. **Prophylactic low molecular weight heparin** should be administered as per local protocols if the patient is admitted.
- 5. **Analgesics** including NSAIDS or paracetamol in conjunction with opioids if needed will be provided for pain relief from pleural procedures and chest drains.
- 6. **Nutritional support** (supplements, dietician referral, nasogastric feeding) should be considered as clinically appropriate.
- 7. **Chest drain management**; for all patients who have chest drain during treatment, flushes and thoracic suction should be used according to local practice.
- 8. **Clinical review** should be conducted every day by the treating physician.

Treatment failure Criteria

During treatment and follow-up, the following objective criteria will be used to record if the patient is failing treatment and requires further intense treatment including re-admission, intrapleural enzyme therapy or surgical intervention. These criteria apply to any patient at any point from randomization to four weeks follow-up, and regardless of which treatment arm they have been randomised to (and applied in general around 72 hours post randomisation for standard care and medium-high RAPID score in the intervention arm and at day 3 +_ 2 days post-discharge for low RAPID score group or at any other time if the treating physician feels they failed medical therapy). This measure is in place to ensure patient safety and objectivity of decision-making.

The treatment failure criteria are **BOTH** of the following:

- 1. The presence of a **significant residual pleural collection** on radiology (chest radiograph, ultrasound and/or CT) as judged by the local investigator AND
- 2. **At least one** of the following criteria (more than one may apply):
 - a. Clinical evidence of **ongoing sepsis** with persistent fever, tachycardia or hypotension.

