9.12.1. Bloods

All blood tests (e.g. CRP, FBC) performed during the RAPTOR f feasibility study are part of the NHS standard care for patients with pleural and systemic infection. These tests will include full blood count, , C-reactive protein, and liver and renal function tests which are advisable to be taken on alternate days if feasible for the first 7 days and then once or twice per week as deemed appropriate by the treating physician if the participant stays over a week. These samples will be processed at each recruiting centre via normal laboratory processes. The results will be recorded on the case reports form.

In addition, all participants will be asked for specific consent for collection of repeated samples of blood (10 millilitres, about 2 teaspoonfuls) on days 1 (randomisation day), 3 and 5 post -randomisation from all centres (Optional) if these are convenient to collect (e.g. if the patient has been discharged home, they will not be collected or day o sample only) and to avoid any discomfort for the patients all research samples will be collected at the same time of usual care samples. We will assess the levels of the biomarkers, including suPAR (Soluble Urokinase Plasminogen Activator Receptor) and PAI-1 (Plasminogen-Activator Inhibitor-1), cytokines (Interleukins (IL) 1 and 2, and NE (Neutrophils elastase) assessments at baseline from all participants at baseline and we will repeat the measurement on day 3 and 5 if applicable and participant willing to donate the samples.

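### Outcome 15 treats day 1, 3 and 5 biomarker samples alike as predictors of treatment failure, with no rule that a sample precede the failure decision or enzyme exposure

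*Protocol*

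**What the plan says.** **Biomarker question.** Outcome 15 (protocol section 6, repeated in the synopsis) measures elevated biomarker levels "in serial samples taken on day 1 (randomisation day), 3 and 5 (post - randomisation) who did not respond to medical treatment". The lay summary (section 2.2) says the aim is to "evaluate whether rising levels of these biomarkers will predict treatment failure", so the later samples are part of the predictor.

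**Sampling.** A footnote to the section 9 schedule says research samples "will be collected on day 1 (randomisation day) 0,3 and 5 post- randomisation (with the first week"; both a day 1 and a 0 appear. Section 9.12.1 plans "assessments at baseline from all participants at baseline", with repeats on days 3 and 5 where possible. Sections 9.12.1 and 9.12.2 make the samples optional, draw them alongside routine samples, and stop them once the patient is home.

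**Failure.** Section 9.7 says its failure criteria are "applied in general around 72 hours post randomisation for standard care and medium-high RAPID score in the intervention arm". Standard-care review "will occur 48 to 72 hours after randomisation and initial above treatment". For RAPID scores 3 to 7, section 9.7 has "the need for surgery clinically revisited at 48 hours post-randomisation". The same section lets failure be recorded at any time up to four weeks. Outcome 5 defines non-response differently: drainage and enzymes have not worked and surgery is required.

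**Enzymes.** In the intervention arm at RAPID 3 to 7, enzyme therapy "should be started as soon as possible after drain insertion and randomisation", unless contraindicated. Standard-care patients receive it only as one form of escalation after a poor response, and low-risk patients only if they fail.

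**Analysis.** Section 13 states that no separate SAP will be used, and section 13.1 contains no biomarker analysis. The wording of outcome 15 is therefore the whole plan on this point.

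**The concern.** A predictor has to be measured before the event it predicts. Outcome 15 sets no such order. A day 3 or day 5 level drawn after failure has been called, or after escalation, would count as predictive on the same footing as a day 1 level.

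Enzyme exposure adds a second problem because it arises differently in the two arms. In the RAPID arm, a patient on enzymes by day 3 is mostly there by allocation. In standard care, such a patient has already responded poorly. The link to at least one marker can be read from the protocol's own names: PAI-1 is an inhibitor of plasminogen activator, and one of the two instilled drugs is a plasminogen activator. An association between later levels and failure could therefore reflect failure itself, its treatment, or the allocated drug.

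The same question reaches back to day 1. Research samples wait for routine samples while enzymes start promptly after randomisation, and no sentence puts the sample first.

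**Working it through.** Outcome 15 has no sample size or other figure of its own to reproduce. The protocol's one calculated figure, 264 patients for a later trial on length of stay (section 13.2), reproduces at 132 per arm but has no bearing here. The check is to put sampling, failure assessment and enzyme exposure on one clock, in hours after randomisation.

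**1. Sampling times.** If randomisation day is day 1, time = (day − 1) × 24. If days are counted from randomisation, time = day × 24.

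| Sample | Randomisation day = day 1 | Days counted from randomisation |
|---|---|---|
| Day 3 | (3 − 1) × 24 = 48 h | 3 × 24 = 72 h |
| Day 5 | (5 − 1) × 24 = 96 h | 5 × 24 = 120 h |

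**2. Usual failure assessment (section 9.7).** Standard-care review is at 48 to 72 h, the criteria are generally applied at about 72 h in standard care and RAPID 3 to 7, and surgery is reconsidered at 48 h in RAPID 3 to 7. The usual window is 48 to 72 h.

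**3. Comparison.**
- Day 3 at 48 h: from 0 to 24 h before the decision.
- Day 3 at 72 h: from 0 to 24 h after the decision.
- Day 5 at 96 h: 96 − 72 = 24 h to 96 − 48 = 48 h after.
- Day 5 at 120 h: 120 − 72 = 48 h to 120 − 48 = 72 h after.

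Day 3 often coincides with the usual decision. Day 5 follows it by 24 to 72 h.

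**4. Low-risk RAPID group.** Discharge is at 24 to 48 h after admission (assumed close to randomisation) and review is 1 to 5 days later. That gives 24 + 24 = 48 h to 48 + 120 = 168 h. These patients are usually home by then, so most have no day 3 or 5 sample.

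**5. Enzyme exposure by day 3.** Section 13.2 puts 50% of the RAPID arm at low risk, so 15 × 0.5 = 7.5, or about 7 to 8 patients, are due enzymes by allocation before any contraindications. That is 7.5 / 30 = 25% of all participants. In standard care the number is zero until escalation. The protocol gives no rate for escalation by day 3. Borrowing the 20% failure rate in section 5 as an assumption gives 15 × 0.2 = 3 patients escalated to enzymes or surgery (1.5 to 6 for an assumed 10% to 40%).

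**6. Day 1.** The pre-randomisation list in section 9.4 does not include research samples. Section 9.12 ties them to routine samples, not to the first dose. The section 9 schedule puts them in the baseline/randomisation column and enzymes in the inpatient column. A pre-dose sample looks intended but is not secured.

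**7. Analyte.** Outcome 15 names NET. The lay summary, the abbreviations and sections 9.12.1 and 9.12.2 all specify neutrophil elastase (NE).

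**The case against.** A reader might infer that day 3 and day 5 samples cannot predict failure at all. The documents do not support that. Section 9.7 allows failure to be recorded up to four weeks. Under outcome 5, a standard-care patient escalated to enzymes at 72 h has not yet failed, and surgery after failed enzymes can come after day 5. The synopsis gives standard care 3 to 5 days (72 to 120 h) before referral, which is later than section 9.7. If randomisation day is day 1, day 3 can precede the usual decision by up to a day. Samples from low-risk patients usually precede their post-discharge review. All of this stands. It shows that some later samples come before failure, not that the plan separates them from those that do not.

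A reader might also infer that the day 1 sample is taken after a dose. Nothing says so. The schedule points the other way, and section 8.3 excludes patients already given enzymes for this infection. The defect is a missing sequencing rule.

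The 20% failure rate in section 5 relates to treatment that includes enzymes. The 30 × 0.2 = 6 failures it implies therefore cannot be placed on the 48 to 72 h clock as if enzymes were the rescue, and no such count is relied on here.

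Finally, no rule carries a biomarker forward or drops it, and biomarkers are absent from the progression table in section 13.1. That limits the consequence. Nor should prediction rest on day 1 alone, since the stated interest in rising levels needs serial samples.

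**Conclusion.** The concern holds in limited form. Outcome 15 uses samples from three days as if all preceded failure. On the usual section 9.7 timetable, day 3 often coincides with the decision and day 5 usually follows it by 24 to 72 h. About a quarter of participants are due enzymes by allocation by day 3, while in standard care enzyme exposure signals a poor response. Later levels are therefore mixed with allocation in one arm and with failure in the other, and with no separate SAP nothing else in the plan sorts this out.

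This rests on the protocol's 50% low-risk share, on failure being assessed when section 9.7 says it usually is, and on either reading of the day count. It does not depend on how strongly enzymes shift each assay, which the documents do not show. NET versus NE is a separate labelling conflict; the repeated use of NE suggests a slip.

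It is worth correcting because a missed pre-dose sample cannot be recovered. The size is modest: this is a secondary outcome with optional sampling in a 30-patient feasibility study, and the primary feasibility conclusions are unaffected.

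**What to change.** 1. In outcome 15, state which failure definition applies, the section 9.7 criteria or outcome 5. Reconcile the day numbering (day 1 versus 0) across outcome 15, the schedule footnote and section 9.12.
2. In section 9.12, take the day 1 research sample before the first enzyme dose where this does not delay treatment, for example from fluid already obtained, with consent. Record each sample time relative to the first dose, the failure call and any escalation.
3. Make the pre-enzyme day 1 level the main predictor and compare patients who did and did not fail. Keep the rising-levels question through a landmark: at day 3 and day 5, include only patients not yet failed or escalated, count only failures after the sample, and show results by enzyme exposure. Report all other day 3 and 5 levels descriptively.
4. Use one analyte name, NE or NET, in outcome 15 and section 9.12.

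The cost is a few sentences in outcome 15 and section 9.12 and extra time fields in the eCRF. Fewer samples will count towards prediction, including day 1 samples that turn out to follow a dose. No treatment rule changes.
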